# 1 LIST OF ABBREVIATIONS

ACE	Angiotensin converting enzyme inhibitors
AE	Adverse event
ALT	Alanine transaminase
AR	Adverse reaction
ARB	Angiotensin II receptor blocker
ASAT	Aspartat aminotransferase
ATC	Anatomical Therapeutic Chemical
BMI	Body mass index
BP	Blood pressure
BW	Body weight
CE	Capillary electrophoresis
CI	Confidence interval
CF	Classification factor
CABG	Coronary artery bypass grafting
CKD	Chronic kidney disease
CKD273	Proteomic urine biomarker including 273 peptides significant for CKD
CKD-EPI	Chronic Kidney Disease Epidemiology Collaboration
CRO	Contract research organization
CRP	C-reactive protein
CTCAE	Common terminology criteria for adverse events
CVD	Cardiovascular disease
DCCT	The diabetes control and complications trial
DM	Diabetes mellitus
DN	Diabetic nephropathy
DSUR	Development safety update report
EC	Ethics committee
eCRF	Electronic case report form
EDTA	Ethylenediaminetetraacetic acid
eGFR	Estimated glomerular filtration rate
EMA	European medicines agency
ESI-TOF	Electrospray-ionization-time of flight
ESRD	End-stage renal disease
EudraCT	European Union Drug Regulating Authorities Clinical Trials
FP7	Framework Program 7
GLA	Glasgow team
GCP	Good clinical practice
GMP	Good Manufacturing Practices

---

GFR	Glomerular filtration rate
GP	General practitioner
hCG	Human chorionic gonadotropin
HCTC	Hannover Clinical Trial Center GmbH
IB	Investigator's Brochure
ICF	Informed Consent Form
ICH	International Conference on Harmonization
IFCC	International Federation of Clinical Chemistry and Laboratory Medicine
IEC	Independent ethics committee
IIT	Investigator initiated trial
IMP	Investigational medicinal product
IPR	Intellectual property rights
IWRS	Interactive web response system
MARVIN	The electronic case report form software program
MDRD	Modification of diet in renal disease
MedDRA	Medical Dictionary for Regulatory Activities
MI	Myocardial infarction
MS	Mass spectrometry
NCA	National competent authority
NYHA	The New York heart association classification for heart failure
PI	Principal Investigator
PTCA	Percutaneous transluminal coronary angioplasty
R	Randomization
RAAS	Renin angiotensin aldosterone system
RAS	Renin angiotensin system
SAE	Serious adverse event
SAP	Statistical analysis plan
SAR	Serious adverse reaction
SD	Standard deviation
SEM	Standard error of the mean
SmPC	Summary of product characteristics
SOC	System organ classes
SOP	Standard operating procedure
SSAR	Suspected serious adverse reaction
SUSAR	Suspected unexpected serious adverse reaction
T	Treatment
UACR	Urine albumin creatinine ratio
UAER	Urine albumin excretion rate
WHO	World Health Organization

## 2 SYNOPSIS

Study title	Proteomic prediction and Renin angiotensin aldosterone system Inhibition prevention Of early diabetic nephropathy In Type 2 diabetic patients with normoalbuminuria
Short term	PRIORITY
Study code of the sponsor	3004
EudraCT number	2012-000452-34
Sponsor	Steno Diabetes Center Senior Investigator, [name] MD. DMSc [name] [name] Denmark [contact] [contact]
International coordinating investigator	Senior Investigator, [name] MD. DMSc Steno Diabetes Center [name] [name] Denmark [contact] [contact] E-mail:[contact]
Indication	Patients with type 2 DM and normoalbuminuria
Objectives	
Primary objective: To confirm that urinary proteomics can predict development of microalbuminuria (as a surrogate marker for the development of overt nephropathy) in a cohort of 2000 type 2 diabetic patients with normal urinary albumin excretion.
 
Secondary objectives: To investigate if early initiation of preventive therapy with spironolactone 25 mg once daily reduces risk of transition to microalbuminuria in those patients identified by urinary proteomics to be at high risk Assessment of safety in the intervention group.
 
Additional scientific objectives: To compare the rate of change in urinary albumin excretion rate in high- vs. low-risk patients (based on the proteomic test), and to compare the effect of spironolactone on rate of change in UACR in the intervention study.

	
In addition, the objective is to study the rate of change in eGFR in relation to urinary marker pattern (CKD 273) and the intervention with spironolactone.
 
To study the ability of urinary proteomic patterns to predict cardiovascular or renal events during the study as well as response to intervention in relation to study endpoints.
 
To establish a biobank that will allow testing of additional putative markers for progression of diabetic nephropathy, development of cardiovascular events and death

Study design/	Prospective, multicenter, randomized, double blind, placebo-controlled phase II-III trial and a prospective observational study.
Study centres	Approx. 17 centres in Europe.
Schedule	
Duration of the entire study (first patient in to last patient out): approximately 4.4 years
 
Study-related: Recruitment period: From March 2014 to August 2016
 
Patient-related: Duration of interventional/observational period including: 104-230 weeks

Number of patients	
Screening: Estimated to be n = 2700
 
To be included: n = 2000
 
To be randomized: n = 300
 
n = 300 patients will be randomized into intervention group with placebo or spironolactone and enter the double-blind treatment period if a CKD273 specific (high risk) proteomic pattern is observed. Patients will be stratified in the two treatment arms (1:1) based on whether or not the patients is treated with RAS blocking agents at the time of entry (Screening). The remaining patients with a negative (low risk) proteomic pattern will be observed regarding the development of microalbuminuria and will receive standard of care treatment (observational group).

Investigational medicinal products	
Investigational medicinal product (IMP):
 
Administration: orally
 
Active medication:
 
Spironolactone (potassium sparing diuretic) Dosage: 25 mg per day (One tablet once daily)
 
Placebo: Dosage: matched placebo (One tablet once daily)

Study endpoints	
Primary study endpoint: Development of confirmed microalbuminuria (UACR>30 mg/g) in at least two out of three first morning voids with <math>\geq 30\%</math> increase (geometric mean)

	
in UACR from “run-in” period samples OR > 40 mg/g (geometric mean).
 
Secondary study endpoints: Changes in albuminuria throughout the study period in all patients by assessing the slope of albuminuria.
 
Predictive value of the urinary proteomics test in regards to renal and cardiovascular events.
 
Changes in eGFR including development of eGFR < 60 ml/min/1.73m^2
 
Changes in retinopathy and frequency of laser treatment.
 
Additional scientific endpoints: The analysis will consider age and gender effects on the predictive value of the proteomics test and treatment effect.
 
Assessment of safety in the intervention group.

Inclusion criteria	
 
1) Written informed consent must be provided before participation. Patient information and consent form must be approved by relevant independent EC. Specifically, all participating patients will be asked to give informed consent for long-term follow-up and collection of follow-up data
 
2) Male or female patients ≥ 18 years and < 75 years of age at Screening visit
 
3) Type 2 DM (WHO criteria)
 
4) Persistent normoalbuminuria (at least 2 of 3 UACR < 30 mg/g samples from “run in”-period)
 
5) eGFR >45 ml/min/1.73m^2 at Screening visit
 
6) The patient must be willing and able to comply with the protocol for the duration of the study
 
7) Female without child-bearing potential at the screening visit. Defined as one or more of following: 
 
7.1)Female patients ≥ 50 years of age at the day of inclusion, who have been postmenopausal for at least 1 year
 
7.2)Female patients < 50 years of age at the day of inclusion, who have been postmenopausal for at least 1 year and serum FSH levels > 40 mIU/mL as well as serum estrogen levels < 30 pg/ml or a negative estrogen test.
 
7.3)6 weeks after surgical sterilization by bilateral tubal ligation or bilateral ovariectomy with or without hysterectomy.
 
 
OR a negative urine pregnancy test at the Screening visit AND one or more of following:
 
 
7.4)Correct use of reliable contraception methods. This includes one or more of the following: hormonal contraceptive (such as injection, transdermal patch, implant, cervical ring or oral) or an intrauterine device (IUD) OR correct use of double barrier with one of the following: barrier methods (diaphragm, cervical cap, Lea contraceptive, femidom or condom) AND in combination with a spermicide.
 
7.5)General sexual abstinence from the time of screening/ baseline, during the study until a minimum of 30 days after the last administration of study medication if this is already established as the patient’s preferred and usual lifestyle.
 
7.6)Having only female sexual partners.
 
 
 


Exclusion criteria
	
7.7)Sexual relationship with sterile male partners only
 
 
1) Average of systolic BP < 110 or >160 mm Hg at baseline
 
2) Average of diastolic BP > 100 mm Hg at baseline
 
3) Type 1 DM (WHO criteria)
 
4) HbA1c <6.5% (48 mmol / mol) AND > 5 years of known duration of diabetes type 2 AND never treated with an antidiabetic drug of any kind.
 
5) Current in treatment with more than one RAAS blocking agent (Angiotensin Converting Enzyme inhibitor, Angiotensin Receptor Blocker or Direct Renin Inhibitor)
 
6) Current lithium treatment(ATC: N05AN)
 
7) Known or suspected hypersensitivity to Spironolactone or to any of its excipients.
 
8) Current use of potassium sparing diuretics (ATC: C03D, C03E), such as: Spironolactone, Eplerenone or Amiloride etc.
 
9) Hyperkalemia at Screening: plasma potassium level >5.0 mmol/L or serum potassium level >5.4 mmol/L.
 
10) Hyponatremia determine by the investigator
 
11) Current cancer treatment or within five years from baseline (except basal cell skin cancer or squamous cell skin cancer)
 
12) Any clinically significant disorder, except for conditions associated with type 2 DM history, which in the Investigators opinion could interfere with the results of the trial
 
13) Cardiac disease defined as: Heart failure (NYHA class III-IV) and/or diagnosis of unstable angina pectoris and/or MI, stroke, PTCA or CABG within the last 3 months
 
14) Diagnosis of non-Diabetic CKD current or in the past
 
15) Diagnosis of liver cirrhosis with current impaired liver function within the last 3 years.
 
16) Diagnosis of Addison's disease.
 
17) Being lactating.
 
18) Intend to become pregnant within the duration of the study or not use adequate birth control.
 
19) Known or suspected abuse of alcohol or narcotics
 
20) Not able to understand informed consent form
 
21) Participation in any other intervention trial than PRIORITY or a related sub-study is not allowed within 30 days before inclusion or concurrent to this study
 


Statistical rationale
	
The aims of the study are to investigate the time to development of the primary endpoint in the included patients. The patients will be based on the urinary proteomic test be divided into low risk patients who will enter an observation study without specific intervention, and high risk patients who will be randomized in a double blind parallel trial comparing placebo with active treatment with spironolactone. It is our hypothesis that high risk patients will develop the endpoint more frequent than low risk patients, and that treatment with spironolactone can mitigate the increased risk in high risk patients.
 
The null hypotheses are that high and low risk patients develop the endpoint with the same frequency, and that the development is similar in patients treated with placebo or spironolactone
 
Sample size calculation:

	
The expected relative proportions of diabetes type 2 patients developing microalbuminuria in our study population are: 24% in patients at high-risk for diabetic nephropathy in the treatment group, 40% in those patients at high-risk for diabetic nephropathy in the placebo group and 8.5% in those therapy-naive patients at low-risk for diabetic nephropathy. Using the samples size formula for two proportions test (<math>\alpha=0.05</math> <math>\beta=0.80</math>), randomized (1:1), <math>n=129</math> in each arm of the intervention group. To account for drop-outs we plan to randomize 300 in all. It is expected that approx. 15% of the population will show a pattern of high-risk of CKD, therefore 2000 patients have to be included. Equal drop-out frequency is expected in both groups and there will be no replacement of drop-out. Discontinuation prior randomization is categorized screening failure.
 
Analysis populations: The primary analysis will be conducted for all patients included (intent-to-treat population) in the observational and intervention study groups. In addition, all relevant efficacy endpoints will be also analyzed for the per protocol population in both study groups.
 
Analysis of primary endpoint: Cox regression analysis of development of the primary endpoint adjusted for age, gender, study site will be conducted in both study groups (observational and intervention) and for study intervention in the interventional group. Secondly adjusted in addition for baseline UACR, HbA1c and BP.
 
Analysis of secondary endpoints: Cox regression analysis of development of secondary endpoints in the both study groups (observational and intervention) as well within the interventional group (high- vs. low-risk), adjusted for age, gender, study site and study intervention with secondary adjustment for baseline UACR, HbA1c and BP.
 
Assessment of safety: The assessment of safety will be based primarily on the frequency of eCRF-documented AEs, laboratory abnormalities, and SAEs (see section 13.3). Occurrence and frequency of eCRF-documented AEs, SAEs and laboratory abnormalities will be summarized by treatment group.
 
In addition AEs leading to death and AEs leading to discontinuation of study medication and/or withdrawal will be summarized for the two treatment groups.
 
Final analysis plan: Statistical analysis of the data will be performed by Steno Diabetes Center. A statistical analysis plan will be written and signed before database lock and unblinding of the entire treatment code.
 
Methods for imputation and type of censoring will be clarified in the statistical analysis plan prior to database lock and unblinding.

--	---

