Blood pressure and glycemic control with pharmacotherapeutic intervention as well as life style interventions are the cornerstones of type 2 DM management aiming at prevention of microvascular complications (9;10). Specific therapy, particularly treatment with angiotensin converting enzyme inhibitors (ACE) and angiotensin receptor antagonists (ARB) to prevent progression to overt proteinuria and advanced stages of diabetic nephropathy is recommended if microalbuminuria is present (11;12). Studies aiming for earlier prevention of nephropathy by starting renin angiotensin aldosterone system (RAAS) blocking treatment in normoalbuminuric patients have given mixed and often disappointing results (13). This might reflect that a large fraction of normoalbuminuric patient may not be at risk for progression thereby reducing the event rate or power in previous studies (14). Early identification of normoalbuminuric patients at high risk for development of diabetic nephropathy could identify patients who might benefit of intervention with increased blockade of the RAAS. Furthermore, blockade of the RAAS with aldosterone blockade has been demonstrated to reduce urinary albumin excretion with 20-30% on top of standard anti-hypertensive treatment including ACE or ARB in proteinuric type 1 and 2 diabetic patients, and a 60% reduction was seen in microalbuminuric type 1 diabetic patients (15;16). Therefore, it may also hold the potential to reduce the risk of development of microalbuminuria in high risk normoalbuminuric patients.

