### 12.4 Albuminuria treatment

All participants included in the trial are normoalbuminuric (UACR <30 mg/g). If a participant reaches the primary endpoint during the course of the study, the information will be flagged in the eCRF and the investigator will be notified.

Participants not in treatment with ACE or ARB at the time of screening should not start treatment before the primary endpoint is reached.

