6.1.2 Secondary outcome

- A. Comparison of composite fatal and non-fatal cardiovascular outcome (MI, stroke, CABG, PTCA, hospitalization for heart failure and CVD) and all-cause mortality during the study.
- B. Comparison of incidence of retinopathy and frequency of laser treatment. Data collected from self-reported AEs.
- C. In addition to the categorical analysis of UACR, an analysis will be performed with changes in geometric mean of UACR throughout the study period in all patients by assessing the slope of albuminuria changes and absolute changes from inclusion to end of trial.
- D. Development of microalbuminuria (UACR >30 mg/g) in at least one morning void urine sample will be used as a secondary outcome instead of confirmed microalbuminuria.
- E. Development of macroalbuminuria (UACR >300 mg/g) in 2 out 3 first morning void urine samples).
- F. For patients with eGFR ≥ 60 ml/ min/ 1.73 m² at baseline, development of eGFR <60 ml/min/1.73m².
- G. Development of CKD stage 4 (eGFR <30 ml/min/1.73m²).
- H. Change in eGFR (slope) from baseline and from three-month post-baseline to end of study.
- I. Change in eGFR (40 % reduction) from baseline and from three-month post-baseline to end of study.
- J. Safety: Adverse Events and Serious Adverse Events. Adverse Events leading to death or discontinuation of study medication and/or withdrawal.
- K. Event of hyperkalaemia with potassium level in plasma ≥ 5.5 mmol and/or ≥ 5.8 mmol in serum at any time point.

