6.3.1.2 Analysis of secondary endpoints

Based on a 2x2 table included the primary endpoint (event/ event free) vs. risk stratification ("high"/- "low"-risk) we will calculate sensitivity, specificity and numbers need to screen for CKD273 and tested for significance using Chi-square test. In a logistic model we will added value using AUC and ROC with comparison between "high"- and "low"-risk vs. event and event-free for both primary endpoint. The logistic models will be performed both unadjusted and adjusted for age, gender, HbA_{1c}, systolic blood pressure, retinopathy, eGFR and UACR at baseline.

For the Cox-regression model a model, including adjustment for age, gender, Hba1c, systolic blood pressure, retinopathy eGFR and UACR at baseline will be comprised for secondary endpoints (see section 6.1.1 and 6.1.2, excluding 6.1.2 C, H and J).

For further clarification of the added value for discrimination, the rIDI will be calculated based on all above described Cox-regressions models with a significant HR for CKD273 in the unadjusted model for each endpoint.

To evaluate changes in UACR and eGFR over time (outcome measurement C and H in section 6.2.1) a linear mix model will be applied with adjustment for eGFR and UACR at baseline.

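### The SAP's UACR slope (outcome C) includes values after endpoint-linked ACE/ARB starts, names no estimand for this, and drops the protocol's handling of RAAS changes and its placebo-first comparison

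*Protocol*

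**What the plan says.** - **Outcome.** The protocol synopsis lists "Changes in albuminuria throughout the study period in all patients by assessing the slope of albuminuria". SAP 6.1.2 C repeats it as "changes in geometric mean of UACR throughout the study period in all patients by assessing the slope of albuminuria changes", together with absolute change to the end of the trial. SAP 6.2 rules out censoring, and neither document stops UACR collection or cuts the slope at the primary endpoint.
- **ACE/ARB after the endpoint.** Protocol 12.4 says "Participants not in treatment with ACE or ARB at the time of screening should not start treatment before the primary endpoint is reached". When a participant reaches it, "the information will be flagged in the eCRF and the investigator will be notified". Protocol 4.1 says that ACE/ARB treatment "is recommended if microalbuminuria is present".
- **Another route.** Protocol 12.3 accepts RAS blockers when indicated for blood pressure and does not mention the endpoint.
- **What the protocol planned.** Section 15.6 adds adjustment for significant changes in RAAS blockade during the study. Section 15.7 applies the primary-endpoint adjustments to the slopes. It also orders the high-versus-low comparisons: high-risk placebo against low risk first, then all high-risk patients.
- **What the SAP does.** Section 6.3.1.2 says that for outcome C "a linear mix model will be applied with adjustment for eGFR and UACR at baseline", and 6.3.2.2 uses the same model for active versus placebo. Section 6.3.1.2 works in the observational cohort, which SAP 4.3.2 defines as everyone with a valid score and baseline data, so both high-risk arms are in it. The placebo-only comparisons in SAP 6.3.1.3 and 6.4 concern the primary endpoint or are Cox models. None covers the slope.

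**The concern.** The event that opens the way to a UACR-lowering drug is defined by UACR, the variable whose slope is then estimated. High-risk patients should reach it more often than low-risk patients. They should also reach it sooner, because UACR is sampled every 13 weeks in high-risk and yearly in low-risk patients. A step down in UACR after the event flattens the fitted slope of the fastest progressors. Baseline eGFR and UACR cannot account for a treatment that starts later because of the outcome.

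Protocol 5.3 and SAP 2.3.3 name the rate of UACR change in high- versus low-risk patients, and the effect of spironolactone on it, as scientific objectives. If the intended quantity is progression without treatment prompted by progression, both contrasts are pulled toward no difference. If the intended quantity is the slope under whatever care follows, the SAP should say so. At present a reader of the results could not tell which was meant.

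**Working it through.** **1. Is there a figure to reproduce?** The documents give none for the slope. The event rates come from protocol 15.1, where they support n = 129 per arm. The unpooled two-proportion formula gives (1.960 + 0.842)² × (0.40×0.60 + 0.24×0.76) / 0.16² = 129.5, so the rates are used there as stated. The primary-endpoint sample size is not affected by this point.

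**2. Direction.** Planned event rates are p = 0.40 (high-risk placebo), 0.24 (spironolactone) and 0.085 (low risk). At 1:1 the pooled high-risk rate is (0.40 + 0.24)/2 = 0.32. More patients pass the 12.4 threshold where progression is faster, so the downward shift is largest there.

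**3. Size by formula.** A step d in log UACR, at a time uniform over follow-up T, changes the mean least-squares slope by d/T. The group shift is therefore

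shift = p × u × a × ln(1 − r) / T,

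where u is the share off ACE/ARB at screening, a the share of those who start after the event, and r the UACR reduction. The documents give none of u, a or r. Assumed: u = 0.2-0.6, a = 0.8, r = 0.15-0.40, and T = 3 years (the documents allow 2 to 4.4).

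Middle case (u = 0.4, r = 0.30): 0.4 × 0.8 × ln(0.70)/3 = −0.0381. Multiplied by p this is −0.0152 for placebo, which is −1.51% per year.

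| Shift in slope, % per year | Low inputs | Middle | High inputs |
|---|---|---|---|
| High-risk placebo | −0.35 | −1.51 | −3.22 |
| Spironolactone | −0.21 | −0.91 | −1.94 |
| Low risk | −0.07 | −0.32 | −0.69 |
| Placebo minus spironolactone | −0.14 | −0.60 | −1.27 |
| Placebo minus low risk | −0.27 | −1.19 | −2.52 |

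**4. Relative size by simulation.** All inputs beyond the event rates and the visit schedule are assumptions.

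- *Slopes calibrated to 40/24/8.5% events, inputs as in step 3.* Active versus placebo shrinks by about 1%, 4% and 9%. Placebo versus low risk shrinks by about 1%, 5% and 10%.
- *Assumed log slopes of 0.12 (placebo), −0.02 (spironolactone) and 0.02 (low risk) per year, 30-50% off ACE/ARB, 90% starting, UACR 20-40% lower.* Placebo versus low risk shrinks by 6-22% and active versus placebo by about 2-6%.
- *Random-slope mixed models on similar inputs.* Placebo versus low risk shrinks by about 5-11% in one check and 6-19% in another, which allowed a lag of 0-6 months. A lag matters because protocol 10.9 requires follow-up samples to be shipped only about every six months.

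**5. The SAP's pooled high-versus-low contrast.** This depends on the assumed spironolactone effect.

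- With slopes 0.12, −0.02 and 0.02, the placebo-only difference is 0.12 − 0.02 = 0.10 per year. The pooled difference is (0.12 − 0.02)/2 − 0.02 = 0.03. Pooling alone removes 70% of the contrast. On that small remainder the relative shrinkage from ACE/ARB starts came out at about 14-55% in one check and 23-65% in another.
- With the calibrated slopes the remainder is larger. In the middle case the means go from 0.3138, 0.1873 and 0.0616 to 0.3000, 0.1789 and 0.0599. The pooled difference falls from 0.2506 − 0.0616 = 0.189 to 0.2395 − 0.0599 = 0.180, about 5%. The low and high inputs give about 1% and 11%.

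**6. Leaving out values after a start.** Across the checks this removed between about half and nearly all of the shrinkage, with almost no loss of precision. A model with one random-slope variance for all groups left about 3% in one check.

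**The case against.** **The all-data slope is legitimate.** A slope over the whole study in all patients is a treatment-policy quantity, and neither document calls it natural history. This stands. The gap is that the estimand is not named. A reader might infer that the planned model is simply wrong and should be replaced, but the documents do not support that.

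**The protocol saw the issue.** A reader of the SAP alone might infer that RAAS changes were never considered. Protocol 15.6 and 15.7 show otherwise, and the SAP's loss of that handling is the documentable fault. Restoring a plain covariate would not reliably remove the effect, because the treatment follows from the outcome.

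**Section 12.4 permits and does not direct.** It allows a start after the endpoint, and 12.3 gives a blood-pressure route without reference to the endpoint. Some starts may therefore follow blood pressure, which the slope model does not contain, so missing at random is an assumption. This also stands, but it does not remove the endpoint-linked route.

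**The size is not documented.** A reader might take 6-22% as the loss in the SAP's own contrast, and near-complete recovery (within 1%) as what leaving out late values would achieve. Both come from one set of assumptions for high-risk placebo versus low risk. The SAP contrast pools the arms, and dropping values after ACE/ARB starts does not undo the spironolactone effect in it.

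**Start dates.** Protocol 10.3 says that medication use is documented at visits. It does not say that start dates are recorded, and low-risk visits are yearly.

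**Conclusion.** The concern holds as an unnamed estimand combined with planned handling that the SAP dropped. Values after the primary endpoint enter outcome C, 12.4 ties permitted ACE/ARB starts to that endpoint, and the SAP model does not address it.

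Only the direction follows from the documents. Relative to progression without endpoint-linked starts, both contrasts move toward no difference, provided events fall in the planned order. The relative sizes (1-22% for high-risk placebo versus low risk, about 1-9% for active versus placebo) rest on assumed ACE/ARB use, uptake and UACR effect. The pooled contrast loses a larger share if spironolactone nearly halts or reverses progression, and about the same share (1-11%) if it does not. One secondary outcome is concerned; the primary endpoint is untouched. A cheap improvement is warranted, and a new main analysis is not.

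**What to change.** 1. In SAP 6.1.2 C, state that the all-data slope is the treatment-policy analysis, and keep it as the main model.
2. In SAP 6.3.1.2 and 6.3.2.2, add a prespecified mixed-model sensitivity analysis. It leaves out UACR values from the first visit at which a new ACE/ARB is recorded after the primary endpoint. The value that met the endpoint stays in, because cutting at the endpoint itself would select on a high value.
3. For high versus low risk, run it for high-risk placebo against low risk first and then for all high-risk patients, as in protocol 15.7. Allow group-specific random-slope variances.
4. Report ACE/ARB starts by group, before and after the primary endpoint.
5. Reconcile protocol 12.3 and 12.4 on starting RAS blockers.

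The cost is SAP wording, one more model per comparison and a slightly wider interval. The added analysis relies on missing at random, which starts prompted by blood pressure could breach. It knows the start only to the visit, so to within about a year in low-risk patients.
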